6.2.2.5 Immediate reporting of SAEs by investigator

SAEs must immediately (within 24 hours of the investigator's awareness) be reported to:

[name]. [name], MD Department of Neurology University of Ulm, Germany [contact] [contact]

Both the investigator and the sponsors safety contact will adhere to the requirements of the German GCP-Ordinance (§§12, 13) on documentation and notification.

The initial SAE Report should be as complete as possible including the essential details of patient's identification (screening number, random number), the serious adverse event (medical term, diagnosis), the trial medication and the assessment of the causal relationship between the event and the trial medication. The SAE report must be reviewed and signed by the investigator.

The investigator should provide related additional information on the clinical course and the outcome of each SAE as soon as possible (Follow up report).

The "Serious Adverse Event Form" is provided in the Investigator Site File.

The investigator should also inform the trial monitor in all cases.

The following are not considered to be serious adverse events:

- An event causing a brief visit to a hospital consultation, an open-door or day hospital,
- outpatient treatment in the emergency department although the reason for which this treatment was instituted may be serious, or
- admission to hospital (more than one night in a hospital bed) including surgical operations planned before or during the study if the condition was present before the study and provided that it does not worsen during the study.

The following are considered to be serious adverse events even if they do not comply with the definition:

- Adverse events caused by misuse or overdose,
- Any pregnancy discovered during the study.

Note: a state of pregnancy is an exclusion criterion. Hence contraceptive measures are necessary in women with childbearing potential throughout the study. However if pregnancy is discovered during the study the trial treatment must immediately be discontinued and the pregnancy followed to term.

Worsening of a sign or symptom of the condition under treatment will normally be measured by efficacy parameters. However, if the outcome fulfills the definition of "serious adverse event", it must be reported as such.

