### Warnings and precautions:

- Risk for Hypertensive Crisis and nonselective MAO inhibition above the recommended Doses
- Melanoma (Epidemiological studies have shown that patients with Parkinson's disease have a higher risk (2- to approximately 6-fold higher) of developing melanoma than the general population. Whether the increased risk observed was due to Parkinson's disease or other factors, such as drugs like rasagiline used to treat Parkinson's disease, is unclear)
- Rasagiline may cause lower blood pressure, especially postural hypotension or increase blood pressure in different patients
- Rasagiline may cause or exacerbate hallucinations or potentially other manifestations of psychotic-like behavior

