### Serious adverse event (SAE)

A serious adverse event (SAE) is one that at any dose (including overdose):

- results in death
- is life-threatening
- requires patient hospitalization or prolongation of existing hospitalization
- results in persistent or significant disability/incapacity or
- is a congenital anomaly/birth defect
- is an important medical event.

"Life-threatening" means that the patient was at immediate risk of death at the time of the serious adverse event; it does not refer to a serious adverse event that hypothetically might have caused death if it were more severe.

If the admission is pre-planned (i.e., elective or scheduled surgery arranged prior to start of the trial) or not associated with an adverse event (e.g., social hospitalization for purpose) or results in a hospital stay less than 12 hours, the serious criterion "hospitalization" is not fulfilled. However, it should be noted that invasive treatment during a hospitalization may fulfill the criteria of "medically important" and may be reportable as a serious adverse event dependent on clinical judgment.

"Persistent or significant disability or incapacity" means that there is a substantial disruption of a person's ability to carry out normal life functions. The irreversible injury of an organ function (e.g., paresis, diabetes, cardiac arrhythmia) fulfills this criterion.

Medical and scientific judgment should be exercised in deciding whether expedited reporting is appropriate in situations where none of the outcomes listed above occurred. Important medical events that may not be immediately life-threatening or result in death or hospitalization but may jeopardize the patient or may require intervention to prevent one of the other outcomes listed in the definition above should also usually be considered serious. Examples of such events include allergic bronchospasm requiring intensive treatment in an emergency room or at home, convulsions that do not result in patient hospitalization, or the development of drug dependency or drug abuse. A diagnosis of cancer during the course of a treatment should be considered as medically important.

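### Section 6.2.2.5 declares emergency-department and day-hospital care not to be an SAE, against the SAE definition in 6.2.2.1, so 24-hour reports of medically important events could be missed

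*Protocol*

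**What the plan says.** Section 6.2.2.1 makes an adverse event serious if it meets any one of six criteria: death, threat to life, hospitalisation or its prolongation, lasting or significant disability, congenital anomaly, or important medical event. The footnote to the last criterion covers "Important medical events that may not be immediately life-threatening or result in death or hospitalization but may jeopardize the patient", and says these should usually be considered serious. Its examples include "allergic bronchospasm requiring intensive treatment in an emergency room or at home, convulsions that do not result in patient hospitalization". The footnote on hospitalisation deals with short and planned stays. If an admission "results in a hospital stay less than 12 hours, the serious criterion" of hospitalisation is not met, but the footnote warns that the event may still be reportable as medically important.

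Section 6.2.2.5 sets the reporting duty: "SAEs must immediately (within 24 hours of the investigator" becoming aware of them. It then opens a list with "The following are not considered to be serious adverse events". The list has three items: an event leading to a brief consultation, open-door or day-hospital visit; "outpatient treatment in the emergency department although the reason for which this treatment was instituted may be serious"; and an admission planned for a pre-existing condition that does not worsen. A second list names events that count as SAEs whether or not they meet the definition, among them adverse events caused by misuse or overdose. The section closes by requiring that worsening of the condition under treatment be reported as an SAE where its outcome meets the definition.

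**The concern.** The emergency-department item excludes the event from the SAE category while conceding that its cause may be serious. It does not say that only the hospitalisation criterion is in question. An investigator who follows it would not file an SAE report for an event that the definition, two subsections earlier, gives as an example of an SAE.

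The serious label carries the expedited part of the safety system. The 24-hour report in 6.2.2.5 depends on it. So do the SUSAR assessment and 15-day notification in 6.2.2.7, since a SUSAR must first be a serious reaction, and the annual list of serious adverse reactions. The synopsis also names the seriousness of AEs as a safety variable. With about 15 sites, two readings of the same rule can also lead to the same event being classified differently from site to site.

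**Working it through.** There is no figure to reproduce, so the check is a comparison of the text.

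**Step 1. Apply both sections to the same event.**

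| Event | Under 6.2.2.1 | Under the literal text of 6.2.2.5 |
|---|---|---|
| Allergic bronchospasm treated intensively in an emergency room, no admission | Usually serious (named example) | Not an SAE |
| Convulsion treated in an emergency department, no admission | Usually serious (named example) | Not an SAE |
| Life-threatening event treated as an emergency-department outpatient | Serious | Not an SAE |
| Adverse event caused by overdose, treated in an emergency department | Depends on the criteria met | SAE, by the second list |
| Worsening of ALS treated in an emergency department, outcome meets the definition | Serious | SAE, by the closing sentence |

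The first three rows conflict. The last two do not.

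**Step 2. Look for a clause that resolves the conflict.**

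- The heading of the exclusion list and the emergency-department item carry no reservation for the other criteria. The planned-admission item does carry a condition.
- The closing sentence of 6.2.2.5 restores the definition, but only for worsening of the disease under treatment. A drug reaction is outside it.
- Section 6.2.2.4 ties completion of the SAE form to the definition in 6.2.2.1. That supports reporting, but the next subsection then says the event is not an SAE. The two instructions remain opposed.
- The hospitalisation footnote in 6.2.2.1 shows how the narrower rule can be written: a short stay removes one criterion and leaves the rest in force. Section 6.2.2.5 does not use that construction.

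**Step 3. Follow an event in one of the first three rows, if caused by the drug and classed under 6.2.2.5.**

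- SAE form and 24-hour report: not triggered.
- SUSAR assessment: not triggered, because seriousness is a precondition.
- Annual list of serious adverse reactions: event absent.
- AE page of the CRF: event present, since 6.2.2.4 requires all AEs to be documented, serious or not.
- DSMB: event available, since 6.2.2.7 and 10.8 give the board the safety data at three-month intervals without restricting it to SAEs. It would not carry a serious flag.
- AE tables in 7.4: event counted by body system, preferred term, intensity and relationship. The item recording whether it was serious would be wrong.

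**The case against.** The best defence is that the list was meant only to limit the hospitalisation criterion. All three items concern contact with a hospital, the footnote in 6.2.2.1 does the same for short stays, and 6.2.2.4 sends the investigator to 6.2.2.1 for the definition. Read so, the sections agree. That intent is plausible, but the text does not state it. The day-hospital item excludes the event itself and not merely the visit. The companion list is expressly written to depart from the definition, so a site could fairly read the exclusion list in the same way.

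A second defence is that 6.2.2.7 leaves SAE workflow to a separate document, such as a safety manual, which is not available here, and that 6.2.2.5 binds the parties to the German GCP ordinance. This limits what can be said about actual site practice. It does not remove the contradiction in the protocol.

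Several stronger inferences are tempting, and here the defence is right:

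- A reader might infer that these events escape the DSMB. They do not, because all AEs are recorded and the board reviews all safety data.
- A reader might infer that every event treated in an emergency department is lost. Misuse and overdose events stay SAEs, and so does qualifying worsening of ALS.
- Hypertensive crisis might seem the natural example. The protocol's warning reads "Risk for Hypertensive Crisis and nonselective MAO inhibition above the recommended Doses", and 4.1.5 lists the crisis among signs of overdosage. A crisis caused by overdose is kept as an SAE. Allergic reaction, listed in 4.1.3 as a frequent effect of rasagiline, is the better example.
- A reader might infer that many SUSARs would be missed. A SUSAR must also be unexpected, so a reaction already listed qualifies only if its severity is not consistent with the product information. The 24-hour report and the annual list carry no such condition.
- The events would not vanish from the comparison between arms. They stay in the AE tables, and only the serious label is at risk.

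**Conclusion.** The contradiction is real: 6.2.2.5 classes as non-serious some events that 6.2.2.1 classes as serious, including the definition's own examples. Followed literally, the rule could stop the 24-hour report, the SUSAR assessment and entry in the annual list of serious adverse reactions for life-threatening or medically important drug reactions managed without admission. It could also delay their recognition as serious until a routine DSMB review.

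The size cannot be estimated. The protocol gives no rate for such events in the 250 patients over 18 months, and it is not known how many sites would let 6.2.2.5 prevail over 6.2.2.1 and 6.2.2.4. The conflict itself rests on the wording alone. The consequence rests on the assumption that at least some sites apply 6.2.2.5 as written and that no separate safety document corrects it. The primary endpoint, the confirmatory analysis and the sample size are untouched.

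**What to change.** Reconcile the two sections by rewording the list in 6.2.2.5. It should say that an emergency-department, consultation or day-hospital visit does not by itself meet the hospitalisation criterion, and that the event remains an SAE if it meets any other criterion in 6.2.2.1. This applies the logic already in the hospitalisation footnote. It concerns reporting only and changes no treatment.

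The sample SAE form in Appendix III needs no change, since it lists seriousness criteria and shows no emergency-department exclusion. The cost is a one-sentence amendment, a notice to the sites and a few more SAE reports.

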## 6.2.2.6 Immediate Reporting of pregnancy by investigator

Any **pregnancy** diagnosed in a female patient or in the female partner of a male patient during treatment with the investigational product must be reported immediately using the "Pregnancy Reporting Form" to:

[name]. [name], MD Department of Neurology University of Ulm, Germany [contact] [contact]

Pregnancy occurring during the clinical trial, must be reported within the same timelines as a serious adverse event. The outcome of a pregnancy should be followed up carefully and abnormal outcome of mother or child should be reported if any.

### 6.2.2.7 Safety evaluation and Reporting by sponsor

The sponsor will ensure that all legal reporting requirements are met. According to GCP the sponsor is responsible for the continuous safety evaluation of the investigational product(s) and the clinical trial.

The sponsor will conduct the management of SAEs and the expedited reporting as required by German Drug Law (AMG) and GCP regulation (GCP-V). Suspected unexpected serious adverse reactions (SUSARs) and safety issues as defined by GCP-V are determined for expedited reporting. The competent authorities and the ethics committees should be notified as soon as possible but not later than 15 calendar days if the event is non-fatal. In this trial on the fatal disease AL, the mortality is the efficacy endpoint and the integrity of the trial may be compromised when the blind is systematically broken for reporting of mortality related SUSARs. Therefore each mortality case will be treated as disease-related and will not be subject to systematic unblinding and expedited reporting. The reporting of these events will be completed within one month after last patient's last visit.

All investigators will be informed too.

The marketing authorization holder of the IMP has to be informed.

Work flow and procedures concerning SAE management will be described in a separate document (e.g. Safety manual).

During the clinical trial the sponsor will submit the Development Safety Update Report including a list of all serious adverse reactions to the ethics committee(s) and the competent authorities once a year.

The independent Data Safety and Monitoring Board (DSMB) will review the safety data every three month in the ongoing trial with recommendation to the sponsor whether to continue, modify or terminate the trial.

#### 6.2.2.8 Emergency procedures

During and following a patient's participation in the trial, the investigator should ensure that adequate medical care is provided to a patient for any AEs including clinically significant laboratory values. The investigator should inform a patient when medical care is needed for intercurrent illness(es) of which the investigator becomes aware.

#### Emergency Unblinding:

In case of an emergency situation the investigator has the right to open the unblinding envelope, but every effort should be taken to avoid unblinding of patients except the information will be needed for the emergency treatment. Opened envelopes have to be signed, dated and the reason

Final 2.1

for unblinding has to be documented. The envelope has then to be filed in the patient file and the sponsor or the responsible monitor has to be informed.

Additionally the sponsors' safety contact will receive a full set of sealed unblinding envelopes for emergency cases. As well every effort should be taken to avoid unblinding of patients except the information will be needed for the emergency treatment. Opened envelopes have to be signed, dated and the reason for unblinding has to be documented.

No other reason than an emergency may justify unblinding. After unblinding the investigator must note the date, time and reason on the case report form. The investigator must also immediately inform the trial monitor of the breaking of the blind.

Whenever possible, [name]. [name] (LKP) should be contacted before the blind is broken (see also chapter 3.6.2).

### 6.3 Other assessments

#### 6.3.1 Prior and concomitant illnesses

Relevant additional illnesses present at the time of informed consent are regarded as concomitant illnesses and will be documented on the appropriate pages of the case report form (CRF), as well as clinically significant conditions that stopped within the last 5 years. In addition the following items have to be addressed specifically:

- Smoking habits within the last 12 months
- Alcohol consumption

### 6.3.2 Prior and concomitant treatments

All patients entering the study must have been continuously treated with the standard therapy for ALS of 100 mg riluzole for at least four weeks.

Relevant additional treatments administered to the patients on entry to the trial or at any time during the trial are regarded as concomitant treatments und must be documented on the appropriate pages of the CRF.

#### 6.3.3 Genetic testing for polymorphisms in the MAO-B gene

The study drug Rasagiline is a second-generation monoaminooxidase (MAO)-B inhibitor which shows neuroprotective effects. As outlined in section 1, the study drug is registered for treatment of Parkinson's disease (PD). Previous studies showed that there are polymorphisms in the MAO-B gene which have been associated with PD [16] [17] [18]. Based on this observation it will be of interest to scan for these polymorphisms in subjects enrolled in this study. If a treatment effect will be identified in this study, DNA might be extracted from these blood samples to scan the MAO-B gene. This might help to stratify responders and non-responders. It is not planned to test for any other genes. The results from these tests will not be shared with the subjects.

Blood samples collected for genetic testing during Baseline Visit 1 will be double-coded before stored at the sponsor. Blood samples and corresponding DNA will be stored until the samples are exhausted, at the latest for up to 10 years after the study is ended.

# 7 STATISTICS

Details of the statistical analysis of the data collected in this trial will be documented in a Statistical Analysis Plan (SAP) that will be provided by the study statistician and finalized before closing the data base and prior to breaking the blind. The SAP is based on the protocol including all amendments. The document may modify the plans outlined in this protocol; however any major modifications of the primary endpoint definition and/or its analysis will also be reflected in a protocol amendment. Any deviation from the original statistical plan must be described and justified in the final report. The statistical analysis will be conducted using SAS®.

## 7.1 Sample size

The sample size calculation is based on a comparison of two survival curves using the one-sided log-rank test. Following assumptions were made: Type one error 0.025, power 0.80, recruiting time 6 months, length of follow up period 18 months, 18 month survival rate of 70 % in the control group, 18 month survival rate of 85 % in the experimental group. Under the assumption of equal number of patients in each group, this scenario requires 106 patients in each group, i.e.  $2 \times 106 = 212$  patients in whole trial.

A previous study [GERP ALS-Study; pioglitazone in ALS; NCT00690118, clinicaltrials.gov ID] showed a drop-out rate of about 15 %, screening failure was observed in about 10 %. Thus, in total 250 patients have to be allocated (with consideration of a drop-out rate) and a total number of 278 patients have to be assessed for eligibility.

The sample size calculation was performed using SAS® software, version 9.2, procedure power.

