## 3.1 Trial duration and schedule

The estimated duration of the whole trial will be about 36 months: 6 months for recruitment, 18 months for the treatment period and 12 months for cleaning the data, carrying out statistical analyzes, and writing the final study report. The actual overall trial duration or patient recruitment period may vary from this estimate.

The trial duration for each patient is expected to be up to 1 month for screening and 18 months for the treatment period.

The estimated time from first patient in to last patient out will be 24 months. Recruitment of patients will start in Q1, 2013, so the anticipated end of trial of the last patient will be in Q1 2015.

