#### Visit 5 – Final Visit (V5)

Visit V5 will be performed 18 months after visit V1. Any adverse events and changes in concomitant medication will be documented.

Blood samples will be taken for the determination of blood cell count, creatinine, CK, ASAT, ALAT and blood glucose. Body weight, blood pressure and radial pulse will be documented and lung

function will be assessed by measuring the patient's vital capacity. In addition ALSFRS-R and SEIQoL will be performed. The patient will be asked for compliance and will return the study medication of V4. Additionally drug accountability will be performed.

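### The 106 per group for 80% power assumes 18 to 24 months of observation; the visit schedule gives each patient 18 months, where 106 evaluable per group gives about 75% and 250 randomised about 78 to 79%.

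*Protocol*

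**What the plan says.** Section 7.1 describes a calculation "based on a comparison of two survival curves using the one-sided log-rank test", at one-sided alpha 0.025 and 80% power. The inputs on timing and control-group survival are "recruiting time 6 months, length of follow up period 18 months, 18 month survival rate of 70 % in the control group". For the experimental group it assumes that 85% are alive at the same time point. The result is that "this scenario requires 106 patients in each group", or 212 in all. An allowance for about 15% drop-out raises this to 250 allocated. The software named is the SAS power procedure.

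The schedule is laid out per patient. Section 3.1 says: "The trial duration for each patient is expected to be up to 1 month for screening and 18 months for the treatment period". Section 5.1 says: "Visit V5 will be performed 18 months after visit V1". The trial schedule table has no column after month 18 and ticks its end-of-trial row at V5. The last telephone contact is at month 15. After that, only adverse events are collected, for 14 days (section 6.2.2.3).

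The end of survival time is less clearly fixed. Section 2.1 runs it to death or the end of the trial. Section 7.3.1 censors living patients at the date of study termination if that falls after the last visit, and otherwise at the last visit. Neither says whether that end is the patient's own or one date for the whole trial.

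**The concern.** In a log-rank calculation, recruiting time reduces the required number only if early recruits are watched for longer than late ones. With 6 months of recruitment and 18 months of further follow-up to one closing date, the first patient is observed for 24 months and the last for 18, and the extra months add deaths. If every patient's observation ends at month 18, those deaths are not there to count and recruiting time should not enter the calculation.

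The log-rank comparison of deaths is the trial's only confirmatory test, and no interim analysis is planned. If the calculation counts deaths that the schedule does not collect, the stated 80% does not describe the trial as laid out.

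**Working it through.** **Inputs.** From section 7.1: one-sided alpha 0.025, power 0.80, 1:1 allocation, survival at 18 months 0.70 (control) and 0.85 (experimental), recruitment 6 months, follow-up 18 months, drop-out 15%. From section 7.3.1: constant hazard ratio. Assumed here: exponential survival, uniform recruitment.

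**Hazards.** Control: −ln(0.70)/18 = 0.01982 per month. Experimental: −ln(0.85)/18 = 0.00903 per month. Hazard ratio: ln(0.85)/ln(0.70) = 0.456.

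**Expected deaths among 212.**
- Common closing date: with accrual A = 6 and follow-up F = 18, the probability of an observed death is 1 − [exp(−λF) − exp(−λ(F+A))]/(λA). Averaged over the groups it is 0.2563, and 212 × 0.2563 = 54.3 deaths.
- Fixed 18 months: the average is (0.30 + 0.15)/2 = 0.225, and 212 × 0.225 = 47.7 deaths.

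**Reproducing the plan's figure.** The Lakatos method steps through time. In each interval D is the expected number of deaths, φ the ratio of experimental to control patients at risk, and θ the hazard ratio. It sums e = Σ D[φθ/(1+φθ) − φ/(1+φ)] and v = Σ Dφ/(1+φ)², and power is Φ(−e/√v − 1.96). With 6 + 18 months to a common end, 105 per group gives 79.8% and 106 gives 80.2%. The plan's 106 is reproduced exactly. That the SAS procedure uses this method is inferred from the match.

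**The same calculation at a fixed 18 months.** Schoenfeld requires (1.960 + 0.842)²/(0.25 × (ln 0.456)²) = 50.8 deaths. Freedman requires (1.960 + 0.842)² × (1.456/0.544)² = 56.1 deaths. Dividing by twice the average death probability gives the number per group.

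| Method | n per group for 80%, 6 + 18 months | n per group for 80%, fixed 18 months | Power at 106 per group, fixed 18 months |
|---|---|---|---|
| Lakatos | 106 | 121 | 74.7% |
| Schoenfeld | 100 | 113 | 77.5% |
| Freedman | 110 | 125 | 73.3% |

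A comparison of two proportions at month 18 also needs 121 per group (134 with continuity correction). None of these gives 106 at a fixed 18 months. Simulated log-rank tests at 106 per group, fixed 18 months, reject in 75.3 to 75.9% of runs.

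**Power at the planned enrolment, 125 per group, fixed 18 months.**
- 15% loss by month 18, assumed exponential, with drop-outs contributing time until they leave: 78.3% by Lakatos, 78.8 to 79.2% by simulation.
- No loss: 81.3% by Lakatos, 81.9 to 82.1% by simulation.

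**If vital status were instead followed to a common date.** At 106 per group, simulated power is about 81% if the hazard ratio of 0.456 persists after study drug ends at month 18. If the hazards are equal from month 18 onward (an assumption at the unfavourable extreme), it is about 68%, below the 75 to 76% obtained by stopping at month 18.

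**The case against.** Three arguments on the other side carry weight.

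**The 75% is not the trial's power.** A reader might infer that it is. It describes 106 evaluable patients per group, with the other 15% contributing nothing. The plan randomises 125 per group. Section 7.2 keeps every treated patient with a post-baseline assessment in the primary set, section 7.3.1 censors living patients at last contact, and section 10.2 retains the data of those who withdraw consent. Most drop-outs therefore contribute time and deaths until they leave. This stands, and the shortfall at 250 is about 1 to 2 points. Inflating 242 to 242/0.85 = 285 likewise treats drop-outs as contributing nothing, so it does not show that 285 must be randomised.

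**A common end date is a possible reading.** Sections 2.1 and 7.3.1 allow it, and section 8.5 ends the trial once all patients have finished treatment or follow-up. It would therefore go too far to say that deaths after month 18 are certain never to be counted. The reading does not rescue the 80%, however. The schedule table places the end of the trial at each patient's V5, and no contact is planned to establish vital status later. The 24 months from first patient in to last patient out equal 6 + 18, so they fit a fixed 18 months per patient equally well.

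**A common close-out is not a safe remedy.** A reader might infer that one extra contact per patient keeps both 106 and 80%. The added months fall after study drug has ended, and the 68% shows that they could lower power. This also stands.

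**Conclusion.** The point holds, at moderate size. The 106 per group for 80% power depends on observation to a common closing date that the schedule does not provide and that the endpoint definition does not clearly fix.

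For a fixed 18 months, the figure on the plan's own evaluable-patient basis is about 75%, with a range of 73 to 78% across formulas; 80% would need 121 per group. For the 250 actually randomised, power is about 78 to 79% with 15% loss and about 81% with none. The drop-out allowance therefore absorbs most of the discrepancy.

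These figures rest on the plan's 70% and 85% survival, proportional hazards, exponential survival and, for the 78 to 79%, exponential loss reaching 15% by month 18. The type I error is not affected.

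**What to change.** - **Section 7.1:** restate the calculation for a fixed 18 months per patient. Give about 75% power for 106 evaluable per group and about 78 to 79% for 250 randomised with 15% loss, and name the method and the loss assumption. If 80% on the evaluable-patient basis is to be kept, the number is 121 per group.
- **Section 7.3.1:** state that patients alive are censored at month 18, or at last contact if earlier. Bring the wording on the end of the trial in section 2.1 into line.
- **If the sponsor prefers follow-up of vital status to a common date:** schedule the contact, and say that 80% at 106 per group then depends on the hazard ratio of 0.456 persisting after study drug stops, with about 68% as the unfavourable case.

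The first two changes cost protocol wording and a slightly less favourable power figure. They require no additional patients or visits.
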